2. STUDY OVERVIEW

2.1. Study Design

This study is a multicenter, double-blind, placebo-controlled study comprised of three periods (Figure 1). Eligible patients will begin a 14-week observational run-in period during which treatment with the standard of care is expected to remain unchanged. At the end of run-in period, patients whose average urine protein (UP) of two valid urine collections is at or higher than 1g/24-h are eligible for randomization into the 36-week double blind (DB) period. Approximately 30 patients are planned to be randomized in a 2:1 ratio, 20 in the cemdisiran arm and 10 in the placebo arm in the DB period, which is followed by a 156-week open-label extension (OLE) period to further evaluate the long-term safety and efficacy. All patients will be followed for safety for 52 weeks after the end of study visit.

The independent Data Monitoring Committee (DMC) will have access to subject level treatment assignments and perform periodic reviews of unblinded data throughout. Details are provided in the DMC Charter of the study.

Figure 1 Study Design

days)	Run-in Period (14 Weeks)		Treatment 1 (36 Wee	Freatment Period (36 Weeks)		sment	Open-label Extension (156 Weeks)		iod	
Screening (up to 120 c	Standard of care	mization (2:1	ALN-CC5 600mg Q4W (n=20) + Standard of care)T k 32)	S ¢ 36)	ndpoint asses	ALN-CC5	DT (c 184) 0S (s 188)	SS (188)	ty Follow-up (2 Weeks)
		Rando	Placebo (n=10) + Standard of care	EC (Wee	EC (Wee	Primary e	+ Standard of care	EC (Week	EC (Week	Safe (5

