5. GENERAL STATISTICAL METHODS

5.1. Sample Size Justification

The sample size of the study was determined based on the precision of the estimate of the treatment effect for the primary endpoint – the percent change from baseline in urine protein/creatinine ratio [UPCR(mg/mg)] as measured in 24-hour urine at Week 32. It should be noted that geometric mean ratio of UPCR at Week 32 to baseline is statistically equivalent to mean of the change from baseline in logarithm of UPCR. Therefore, the effect size of the study is defined as the difference of change from baseline between cemdisiran and placebo in the logarithm of UPCR.

Based on the NEFIGAN study, [Fellstrom 2017] we assume that in the placebo arm the geometric mean ratio of UPCR at Week 32 to baseline is 0.88 (log standard deviation [SD] 0.597), corresponding to a 12% reduction, while the geometric mean ratio is 0.5, or a 50% reduction for the cemdisiran arm. Using these assumptions, sample size of 9 and 18 in the placebo and cemdisiran arms will provide a width of 0.80 (+/- 0.4) for the 90% confidence interval (CI) for treatment effect size estimate (cemdisiran – placebo) in log scale.

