7.2. Secondary Endpoints

For secondary endpoints assessed in DB period, the analysis will compare randomized arms (cemdisiran vs. placebo) using the mITT analysis set.

The secondary endpoints which are assessed beyond Week 36 will be summarized to describe the long-term efficacy of cemdisiran using the All Cemdisiran Treated Analysis Set by treatment sequence, i.e., cemdisiran/cemdisiran, placebo/cemdisiran, and All Cemdisiran.

The planned analyses of the secondary endpoints are summarized in Table 2.

Endpoint	Statistical Method	Notes
Percent of patients with partial clinical remission (urine protein [UP] <1.0g/24-hour) at Week 32	Treatment comparison will be conducted using Cochran-Mantel- Haenszel test stratified by baseline 24- hour UP (≥ 1g/24-hour and <2 g/24-hour	
Percent of patients with >50% reduction in 24-hour proteinuria at Week 32	vs. ≥ 2 g/24-hour). The number and percentage of patients who are responders at Week 32 are summarized by treatment arm.	
	The difference in percentages of responders and corresponding 90% CI based on the Wilson score method with continuity correction will be presented.	

 Table 2
 Summary of Analyses for the Secondary Efficacy Endpoints

Endpoint	Statistical Method	Notes
Percent change from baseline in 24-hour proteinuria (g/24- hour) at Week 32	Treatment comparison and estimates will be conducted by a similar MMRM model used for the analysis of primary endpoint. Descriptive statistics will also be generated by treatment arm at each scheduled visit. Geometric Mean (with 90% CI) figures of the ratio to baseline by treatment arm will be plotted as well as individual spaghetti plots.	
Change from baseline in UPCR as measured in a spot urine at Week 32	The change from baseline in log- transformed spot UPCR by visit through Week 36 will be analyzed via a MMRM model. The model includes log- transformed baseline spot UPCR, treatment, visit, and the interaction of treatment and visit. Robust errors [White 1980] will be used to model the within-patient errors. Descriptive statistics will also be generated by treatment arm at each scheduled visit. Geometric Mean (with 90% CI) figures of the ratio to baseline by treatment arm will be plotted as well as individual spaghetti plots.	Scheduled assessments are outlined in the Table 1 (Schedule of Assessments) of the protocol.

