8. CHANGES TO PLANNED ANALYSES

Change from SAP V1.0	Detailed Description/Rationale
Change the primary and secondary endpoints	Per protocol amendment 3
The working correlation structure in the MMRM model for the analysis of the primary endpoint is changed to unstructured	Since there are only two post baseline assessments, the unstructured working correlation will provide robust estimates by REML.
Section 7.8 and Appendix 10 are added	To address COVID-19 pandemic impact
Various editorial changes	To improve clarity

9. **REFERENCES**

White H. A Heteroskedasticity-Consistent Covariance Matrix Estimator and a Direct Test for Heteroskedasticity. Econometrica. 1980;48(4):817-38.

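### The spot UPCR model uses robust errors with no stated small-sample correction; with about 20 and 10 patients, a nominal 90% interval would cover about 86–88%

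*SAP*

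**What the plan says.** The spot UPCR row of Table 2 (SAP Section 7.2) says that the log change, "transformed spot UPCR by visit through Week 36 will be analyzed via a MMRM model". The model terms that follow log baseline spot UPCR, with the start of the next sentence, read: "treatment, visit, and the interaction of treatment and visit. Robust errors". That next sentence in full is: "Robust errors [White 1980] will be used to model the within-patient errors". The reference (Section 9) is to the heteroskedasticity-consistent covariance estimator. Neither this row nor any other section gives a working covariance for this model, a small-sample correction or a degrees-of-freedom method.

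The row mentions 90% intervals for plotted geometric means. It mentions no p-value. The opening of Section 7.2 says that secondary endpoints in the double-blind period compare the randomized arms.

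On size, Section 2.1 says that about 30 "patients are planned to be randomized in a 2:1 ratio, 20 in the cemdisiran arm and 10 in the placebo arm". Section 5.1 bases its precision statement on slightly fewer: "sample size of 9 and 18 in the placebo and cemdisiran arms will provide a width of 0.80 (+/- 0.4" on the log scale, for a 90% interval. Section 5.5 makes all comparisons descriptive.

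The primary MMRM (Section 7.1) uses an unstructured covariance. Section 8 of SAP Amendment 1 records this: "The working correlation structure in the MMRM model for the analysis of the primary endpoint is changed to unstructured". The reason given is that there are only two post-baseline assessments.

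**The concern.** A sandwich estimator builds the variance from squared residuals. Fitted residuals are on average smaller than the true errors, so without a correction the variance is too small. The shortfall depends on the number of independent patients in each arm and is not cured by more visits per patient. Here the placebo arm, with about 10 patients, carries most of the variance of the treatment difference and most of the bias. If the result is then referred to a normal distribution, or to a t distribution with many degrees of freedom, the noise in the variance estimate is ignored as well.

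The trial was sized on the precision of a 90% interval, so intervals are its main inferential output. A reader will set the spot UPCR interval beside the primary one and assume that both hold their stated level.

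**Working it through.** **Inputs.** Arms of 20 and 10 (Section 2.1) and of 18 and 9 (Section 5.1); SD of the log change 0.597 (Section 5.1, "0.88 (log standard deviation [SD] 0.597"); 90% two-sided level. The number of spot visits is not in the SAP, so 4 and 9 were assumed. The within-patient correlations are also assumed.

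**1. The plan's own figure.** Half-width = 1.645 × 0.597 × √(1/9 + 1/18) = 1.645 × 0.597 × 0.408 = 0.401, width 0.802. The stated 0.80 is reproduced, using a normal quantile.

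**2. Bias of the uncorrected sandwich at one visit.** With equal variances, its expectation relative to the true variance is [(n₁−1)/n₁² + (n₂−1)/n₂²] / (1/n₁ + 1/n₂).

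- 20 and 10: (19/400 + 9/100)/(1/20 + 1/10) = 0.1375/0.15 = 0.917. The square root is 0.957, so the standard error is 4.3% too small.
- 18 and 9: (17/324 + 8/81)/(1/18 + 1/9) = 0.1512/0.1667 = 0.907. The square root is 0.953, so it is 4.7% too small.

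The SD cancels, so the result does not depend on 0.597.

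**3. Coverage.** Approximate degrees of freedom for 20 and 10 are (1/20 + 1/10)² / [(1/20)²/19 + (1/10)²/9] = 0.0225/0.001243 = 18.1; for 18 and 9 they are 16.1. Coverage is the probability that a t variable with those degrees of freedom lies within ± (quantile used × SE ratio). For 20 and 10 with a normal quantile, the limit is 1.645 × 0.957 = 1.575.

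| Arms | Normal quantile | t on N−2 |
|---|---|---|
| 20 and 10 | 86.7% | 87.9% |
| 18 and 9 | 86.3% | 87.7% |

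**4. Simulation of the longitudinal model.** The Table 2 model was fitted with a patient-clustered sandwich and judged on the treatment contrast at the next-to-last visit, with 3,000–4,000 trials per scenario (Monte Carlo error about 0.5–0.6 points). Scenarios varied the visits (4 or 9), the working covariance (independence, compound symmetry, unstructured), the true correlation (compound symmetry or AR(1)) and missing data (none or 10%). Not every combination was run.

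| Arms | Normal quantile | t on N−3 |
|---|---|---|
| 20 and 10 | 85.9–87.3% | 87.1–88.4% |
| 18 and 9 | 85.5–87.4% | 87.1–88.8% |

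For 20 and 10, the error rate at a nominal 10% is 100 − 88.4 = 11.6% to 100 − 85.9 = 14.1%. The placebo-arm LS-mean interval with a normal quantile covers 83–85%.

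**5. With a correction, same simulations.** A Mancl-DeRouen type variance covers 89.3–91.1% with a normal quantile and 90.7–92.2% with t on N−3. An approximation to Kauermann-Carroll with t on N−3 covers 88.8–90.3%. Model-based variance (compound symmetry or unstructured) with t on N−3 covers 89.5–91.1%.

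**The case against.** Several points on the other side stand.

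- **Uncorrected is an inference.** It rests on the citation and the SAP's silence. A correction chosen at programming would remove the problem, but the plan fixes none, and the cited estimator carries none.
- **The affected outputs are few.** The row promises no p-value. Its 90% intervals follow the descriptive statistics and, unlike those in Section 7.1, are not called model-adjusted, so they may be raw. The shortfall applies to whatever is taken from the model.
- **The stakes are low.** This is one secondary endpoint and all comparisons are descriptive. The SAP names no key secondary endpoint.
- **Robust errors are a defensible choice here.** With 9 visits (assumed), an unstructured matrix has 9 × 10/2 = 45 parameters for about 30 patients.

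A reader might infer from the Amendment 1 change that the robust errors were left behind by oversight. The documents do not support that. The spot UPCR row of SAP version 1.0 had no such text. It entered in Amendment 1, together with the change to the primary model, and the reason given for that change (only two post-baseline visits) does not carry over to a model with more visits.

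A reader might also infer that the robust method should give way to a model-based covariance. That is not shown to be better throughout, because a common covariance has its own weakness when the arms differ in spread. In a single-visit check with 20 and 10 patients, pooled model-based t covered 90.1% at equal SDs. It covered 87.4% with a placebo SD 1.25 times the active SD, and 85.1% at 1.5 times. The uncorrected sandwich with t covered 88.0%, 87.8% and 87.4%.

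Finally, the phrase about modelling within-patient errors could be read as a claim that robust errors supply a correlation model. In an MMRM the patient-clustered form is the natural meaning, so this is loose wording and not a separate error.

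**Conclusion.** The point holds in a limited form. If the stated method is followed without a correction, the standard error of the spot UPCR treatment difference is about 4–5% too small and a nominal 90% interval at Week 32 covers about 86–88%, a loss of 2–4 points. Any p-value from the model would be too small to match.

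This assumes the uncorrected patient-clustered form, arms near 20 and 10, and similar spread in the two arms. The visit count and correlations are assumed too, but the result moved little over the range tried. The primary MMRM uses a different variance method and is not affected. Nothing in the documents makes a trial decision depend on this analysis.

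**What to change.** Keep the robust approach and complete its specification in the spot UPCR row of Table 2. Suggested content: standard errors from a sandwich estimator clustered on patient, with a named small-sample bias correction (for example Mancl-DeRouen or Kauermann-Carroll); a named working covariance with a fallback; and intervals, and any p-values, from a t distribution with Satterthwaite or between-patient degrees of freedom. The row should also say whether the plotted 90% intervals come from the model or are raw. A structured REML covariance with Kenward-Roger inference can serve as a sensitivity analysis. That exact combination was not simulated here, and its structure should be chosen against the protocol's visit schedule.

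The cost is one or two sentences, with no new data. Intervals become modestly wider. For 20 and 10 patients, removing the bias alone gives 1/0.957 = 1.04. Moving also from a normal quantile to t on 27 degrees of freedom gives (1.703/1.645)/0.957 = 1.08. Using t on 18.1 degrees of freedom gives (1.734/1.645)/0.957 = 1.10. Mancl-DeRouen with a t reference is slightly conservative (90.7–92.2% in the simulations).

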7.3. Exploratory Analyses

Exploratory endpoints will be summarized descriptively by treatment arms during the DB period using mITT Analysis set.

For the slope of eGFR computed for the entire study period, it will also be analyzed by treatment sequence (cemdisiran/cemdisiran, placebo/cemdisiran) using the All Cemdisiran Treated Analysis Set. However, the other exploratory endpoints may be analyzed over the entire study if deemed appropriate. Table 3 summarizes the planned analyses for exploratory endpoints.

Exploratory Endpoint	Statistical Method	Notes
Change from baseline in estimated glomerular filtration rate (eGFR) ¹ at Week 32	Descriptive statistics of eGFR will be presented by visit and treatment arm. Individual patient data will be presented in spaghetti plots. Shift tables of eGFR categories from baseline to post-baseline visits and an overall worst post-baseline will also be presented.	
The slope of eGFR computed for the first 36 weeks using all assessments during the period	The random coefficient model for eGFR will include baseline eGFR, treatment, time (in year), and the interaction of treatment and time as fixed effects and intercept and time as random effects.	The first study drug dosing will be defined as the time reference point t=0 In addition, the slope of eGFR for each subject will be estimated.
The slope of eGFR computed for the entire cemdisiran treatment period including patients who started on placebo in the DB period then switched to cemdisiran in the OLE period, and those started on cemdisiran in the DB period.	The random coefficient model for eGFR will include baseline eGFR, treatment sequence, time (in year), and the interaction of treatment sequence and time as fixed effects and intercept and time as random effects.	This endpoint will be analyzed only at the final analysis using Cemdisiran Treated Analysis set. The first administration of cemdisiran will be defined as the time reference point t=0.
The slope of eGFR during placebo period comparing the slope during OLE for patients who crossed over from placebo to cemdisiran.	The random coefficient model with piecewise regression will include baseline eGFR, time during the placebo treatment and time during the cemdisiran treatment as fixed effects and intercept and times as random effects.	This endpoint will be analyzed only at the final analysis using placebo/cemdisiran treatment sequence group.
Change from baseline in creatinine clearance at Week 32	Descriptive statistics will be presented by visit and treatment arm.	See section 6.4.3 in the protocol for creatine clearance

Table 3	Summary of	f Analyses	for Exploratory	Endpoints
	e e e e e e e e e e e e e e e e e e e	e e	1 1	1

Exploratory Endpoint	Statistical Method	Notes
Percent of patients in full clinical remission (Urine Protein [UP]<0.3 g/24- hour) at Week 32	The number and percentage of patients who are responders at Week 32 are summarized by treatment arm. The difference in percentages of responders and corresponding 90% CI based on the Newcombe method based the Wilson score with continuity correction will be presented.	
Change from baseline in 24-hour albuminuria at Week 32	Descriptive statistics will be presented by visit and treatment arm.	
Change from baseline in the urine albumin/creatinine ratio (UACR) as measured in 24-hour urine at Week 32	Descriptive statistics will be presented by visit and treatment arm.	
Change from baseline in levels of renal damage, complement activation and inflammation markers over the course of the study	The levels of the biomarkers and their changes and percentage changes from baseline will be summarized descriptively by visit and treatment arm or treatment sequence	

¹ eGFR will be based on CKD-EPI: $eGFR = 141 * \min\left(\frac{Scr}{\kappa}, 1\right)^{\alpha} * \max\left(\frac{Scr}{\kappa}, 1\right)^{-1.209} * 0.993^{Age} * 1.010[if, formala] + 1.150[if, black]. Serie accurate contrained (model) = 0.7 for formal accurate on 0.000$

1.018[*if female*] * 1.159[*if black*]. Scr is serum creatinine (mg/dL), κ is 0.7 for females and 0.9 for males, α is - 0.329 for females and -0.411 for males, min indicates the minimum of Scr/ κ or 1, and max indicates the maximum of Scr/ κ or 1, age is calculated at visit: age at consent + (visit date-consent date)/365.25 and rounded to integer.

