3. OBJECTIVE AND ENDPOINTS

The study objectives and endpoints based on the study protocol are presented Table 1 below.

Endpoints		
• Percent change from baseline in urine protein/creatinine ratio [UPCR] as measured in 24-hour urine at Week 32		
 Percent change from baseline in 24-hour proteinuria (g/24-hours) at Week 32 Percent of patients with partial clinical remission (urine protein [UP] <1.0 g/24-hour) at Week 32 Percent of patients with >50% reduction in 24-hour proteinuria at Week 32 		
 Change from baseline in UPCR as measured in spot urine at Week 32 Change from baseline in hematuria at Week 32 Erequency of adverse events (AEs) 		
• Trequency of adverse events (TES)		
 Change from baseline in estimated glomerular filtration rate (eGFR) at Week 32 The slope of eGFR computed for the first 36 weeks using all assessments during the period The slope of eGFR computed for the entire study period including the open label extension using all assessments during the study. Change from baseline in creatinine clearance at Week 32 Percent of patients in full clinical remission (Urine Protein [UP] <0.3 g/24-hour) at Week 32 		

Table 1Objectives and endpoints

Objectives	Endpoints		
• To assess the incidence of antidrug	• Change from baseline in the urine		
antibodies (ADA)	albumin/creatinine ratio (UACR) as		
	measured in 24-hour urine at Week 32		
	• Change from baseline in C5 level over		
	the course of the study		
	• Change from baseline in complement		
	activity (Complement Alternative		
	Pathway [CAP] and Complement		
	Classical Pathway [CCP]) over the		
	course of the study		
	• Evaluation of area under the curve		
	(AUC), maximum plasma		
	concentration (C_{max}) , time to		
	maximum plasma concentration		
	(T_{max}) , terminal half-life $(t^{1/2})$,		
	clearance (CL/F), volume of		
	distribution (V/F), cumulative amount		
	excreted unchanged in urine (Ae) and		
	percent of dose excreted in the urine		
	(fe) of cemdisiran (25-mer) and 23- mer		
	• Evaluation of AUC, Cmax, Tmax, t ¹ /2.		
	CL/F. V/F. Ae and fe of 22-mer		
	AS(N-1)3'		
	• Change from baseline in levels of		
	renal damage, complement activation		
	and inflammation markers over the		
	course of the study		
	• Incidence of antidrug antibodies		
	(ADA)		

4. **PATIENT POPULATION**

4.1. **Population Definitions**

The following patient populations will be used for analyses:

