• Modified Intent-to-Treat Analysis Set (mITT): All patients who receive any amount of study drug and have baseline and at least one post-baseline 24-hour urine protein creatinine ratio assessment. Patients will be grouped by assigned treatments (i.e., as randomized).

- Safety Analysis Set: All patients who receive any amount of study drug. Patients will be analyzed according to the treatment actually received.
- PK Analysis Set: All patients who receive a full dose of study drug and have at least 1 PK concentration measurement.
- PD Analysis Set: All patients who receive a full dose of study drug and who have at least one post-dose blood sample for the determination of plasma C5 level.
- All Cemdisiran Treated Set: All patients who receive at least one dose of cemdisiran, including patients who take cemdisiran during the DB period and patients who first take placebo during the DB period and switch to cemdisiran during the OLE period.

The primary population used to evaluate efficacy will be the mITT Population unless stated otherwise. Safety will be analyzed using the Safety Analysis Set. The PK and PD Analysis Sets will be used to conduct PK and PD analyses, respectively. The All Cemdisiran Treated Set will be used to summarize long-term efficacy and safety of cemdisiran.

4.2. **Protocol Deviations**

Protocol deviations will be classified into major or minor deviations by medical review. A major deviation is defined as a deviation that may significantly impact the completeness, accuracy and/or reliability of the trial data; that may significantly affect a patient's rights, safety and wellbeing (ICH.E3 R1 Structure and Contents of Clinical Study Reports Guidance for Industry. 2013). Major protocol deviations will be reviewed and approved by Alnylam prior to the interim database lock for the primary analysis of the DB treatment period. All protocol deviations will be presented in a listing. The Sponsor or designee will be responsible for producing the final protocol deviations file. This file will include at a minimum each protocol deviation and whether or not this deviation is classified as a major protocol deviations. This file will be finalized prior to the primary treatment phase database lock. Protocol deviations will be summarized in the CSR.

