5.3. Baseline Definitions

Baseline value for 24-hour UP, UPCR, and UACR will be calculated as the average of two valid (as per section 6.4.1.1 of the protocol) collections at week -2 visit (i.e., the last measurement prior to the first dose of study drug). Baseline values for vital signs will be defined as the assessments at week -2 visit because of the required vaccination when applicable. The baseline value for an ECG variable (heart rate, PR interval, QRS interval, QT interval or QT_c interval) will be the average of last triple assessments prior to the first dose of study drug (Day 1). For other parameters, baseline is defined as the last non-missing value prior to the first dose date/time of the study drug, unless otherwise specified.

For the All Cemdisiran Treated Set, baseline for patients randomized to cemdisiran in DB period is as defined above. For patients who switched from placebo in the DB period and received at least one dose of cemdisiran in the OLE period, baseline for all parameters will be redefined as the last non-missing assessments prior to the first dose of cemdisiran, except for assessments based on 24-hour urine collections where the average of the two valid collections at week 32 visit will be the baseline value and for ECG variables where the average of the last triplet assessments prior to the first dose of study drug in OLE period will be the baseline.

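### The exploratory eGFR slope listed for the whole study has no matching model: the Table 3 row covers cemdisiran time only, and its sequence contrast is not a randomised comparison

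*SAP*

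**What the plan says.** Table 1 in SAP Section 3, which is said to be based on the protocol, lists this exploratory endpoint: "The slope of eGFR computed for the entire study period including the open label extension using all assessments during the study". The text of Section 7.3 keeps that name: "For the slope of eGFR computed for the entire study period, it will also be analyzed by treatment sequence".

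Table 3 in Section 7.3 has no row of that name. Its only long-term row for both treatment sequences is "The slope of eGFR computed for the entire cemdisiran treatment period including patients who started on placebo in the DB period", together with those who began on cemdisiran. The row's note reads "The first administration of cemdisiran will be defined as the time reference point t=0". The model has baseline eGFR, treatment sequence, time and sequence-by-time as fixed effects, with random intercept and time.

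Two other sections determine what goes into that row:
- **Analysis set (Section 4.1).** The All Cemdisiran Treated Set is "All patients who receive at least one dose of cemdisiran, including patients who take cemdisiran during the DB period" and placebo patients who switch in the open-label extension (OLE).
- **Baseline (Section 5.3).** For switchers, baseline eGFR is "redefined as the last non-missing assessments prior to the first dose of cemdisiran".

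Table 3 has two further slope rows: "The slope of eGFR computed for the first 36 weeks using all assessments during the period", by treatment with time zero at first study drug, and a piecewise model in the placebo/cemdisiran group with "time during the placebo treatment and time during the cemdisiran treatment as fixed effects".

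**The concern.** For a placebo patient who switches, a slope that uses every assessment in the study cannot also start its clock at first cemdisiran. Two programmers could follow the SAP and produce different analyses. The one Table 3 specifies does not estimate the endpoint in Table 1.

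The difference goes beyond naming. Once each group's clock starts at its own first cemdisiran dose, both groups are on drug throughout, and whatever a switcher lost during 36 weeks on placebo is absorbed into the new baseline. A sequence-by-time term near zero could then be misread as showing no benefit from earlier treatment, when the model is not built to show one.

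**Working it through.** **1. Design figures.** The SAP gives no precision figure for eGFR slope. Its only one is for UPCR (Section 5.1), and it reproduces: 1.645 × 0.597 × √(1/9 + 1/18) = 0.401, against the stated ±0.4. Nothing below depends on it.

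**2. The endpoint and the row side by side.**

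| Feature | Table 1 and Section 7.3 text | Table 3 row |
|---|---|---|
| Period | Whole study including OLE | Cemdisiran treatment only |
| Time zero | Not stated; whole study implies first study drug | First cemdisiran dose |
| Switchers' baseline | Not stated | Reset before first cemdisiran (5.3) |
| Patients | Not restricted | At least one cemdisiran dose (4.1) |

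For patients randomised to cemdisiran the two clocks coincide. The reset affects only the placebo/cemdisiran group.

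**3. What the row omits.** Section 5.10 starts the OLE at Week 36 and ends it at Week 188. For switchers the row drops 36/188 = 19% of that time. (Taking the stated 156-week OLE at face value, 36/192 is also 19%.) The sequences then contribute about 188 and 188 − 36 = 152 weeks. Placebo patients who never switch contribute nothing to this row.

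**4. What the sequence-by-time term can show.** Assumptions, none from the SAP: eGFR is linear with slope b mL/min/1.73m² per year off drug, and slope b + d from the first cemdisiran dose. Without noise:
- *Table 3 clock.* Both groups have slope b + d, so the expected difference is (b + d) − (b + d) = 0 for any d.
- *Common origin at first study drug, level at Week 188.* The early group has changed by (b + d) × 188/52. The delayed group has changed by b × 36/52 + (b + d) × 152/52. The difference is d × 36/52 = 0.69d, that is 0.69, 1.38, 2.08 and 2.77 mL/min/1.73m² for d = 1, 2, 3 and 4.
- *Common origin, one straight line per group.* Least squares gives a slope difference of about 0.10d per year with 4-weekly visits and 0.12d with 12-weekly visits (visit spacing assumed).

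The 0.69d figure is a difference in level. It is not the size of the effect on the slope named in Table 1, which is much smaller when fitted as a single line.

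**5. Whether another analysis fills the gap.**
- The 36-week slope compares the arms from a common origin but stops at Week 36.
- The piecewise row uses switchers only, with no concurrent comparator.
- The intra-patient comparison in Section 5.10, which includes eGFR, also uses switchers only.

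No planned model compares eGFR between the randomised arms beyond Week 36 from a common origin.

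**The case against.** The strongest reply is that only a label is stale. The two earlier SAP versions in the same file already used the cemdisiran-treated set, time zero at first cemdisiran and a sequence-by-time term for this row. The current version reworded the row's name to fit. Section 5.10 says the final analysis describes long-term efficacy in the All Cemdisiran Treated Set by sequence, and Section 5.7 re-maps switchers' visits to first cemdisiran, so the row is coherent with the rest of the plan. An on-drug slope is a legitimate descriptive quantity, Section 5.5 makes all comparisons descriptive, and the SAP never calls the sequence-by-time term a treatment effect. All of this stands, and it rules out any suggestion that an analysis was removed.

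A reader might also infer that the plan throws away placebo-period eGFR. It does not: the 36-week slope by arm, the piecewise row and the intra-patient comparison all use it. Placebo patients who never enter the OLE are in the 36-week slope if they meet the mITT definition.

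Nor do the documents support saying that the plan destroys its only randomised long-term comparison. No objective of early versus delayed start is stated, and Section 7.1 describes 24-hour UPCR by arm through both periods. The gap concerns eGFR.

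Finally, a model with a slope change at Week 36 is not literally one slope, and after Week 36 it too depends on who enters the OLE. Both points are fair and shape the fix. They do not supply the missing analysis.

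**Conclusion.** The inconsistency holds on the text alone. An endpoint presented as coming from the protocol is named in Table 1 and in Section 7.3, and Table 3 analyses a different quantity with another period, origin, baseline and set of patients. Within that row, 19% of switchers' time to Week 188 and all never-switching placebo patients are left out, and the sequence contrast is not randomised.

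The zero expectation for that contrast, and the 0.69d level difference it cannot see, rest on an assumed linear course and an assumed drug effect d that begins at the first dose. They illustrate the direction of the problem and do not forecast its size.

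The point is limited to one exploratory endpoint reported at the final analysis. Whether the protocol's own method differs cannot be judged from the SAP.

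**What to change.** 1. **Add a row to Table 3 for the endpoint Table 1 names.** Use an exploratory random coefficient model over the entire study, with time zero at first study drug, double-blind baseline eGFR, randomised arm, all treated patients with eGFR data, and a slope change at Week 36 allowed to differ by arm. The change point avoids forcing placebo and drug time in the delayed group onto one line.
2. **Report the arm differences with 90% CIs.** If a single whole-study slope is wanted, define it as the time-weighted average of the two segments, (36 × first slope + 152 × second slope)/188, so that the endpoint is fixed in advance.
3. **State the caveat.** Estimates after Week 36 depend on OLE entry and on missing-data assumptions, and will be imprecise with about 30 patients.
4. **Keep the cemdisiran-period slope as a separately named descriptive row.** Say that its sequence-by-time term is not a treatment effect.
5. **Align the wording of Table 1, the Section 7.3 text and Table 3, and record the change in Section 8.** The only entry there specific to Section 7.3 is an added plot.

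The cost is one extra model at the final analysis, on data already collected, plus edits to three places in the SAP.
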